6.4.3.2 SAEs and Unsolicited AEs

Unsolicited AEs (see Section 11.2.2) will be summarized using MedDRA System Organ Class and preferred terms. Tables will show by treatment arm the number and percentage of participants experiencing an Unsolicited AE within a System Organ Class or within preferred term category by severity or by relationship to study product. For the calculations in these tables, a participant with multiple Unsolicited AEs within a category will be counted once under the maximum severity or the strongest recorded causal relationship to study product. Formal statistical testing comparing arms is not planned since interpretation of differences must rely heavily upon clinical judgment.

A listing of SAEs reported to the DAIDS Regulatory Support Center (RSC) Safety Office will provide details of the events including severity, relationship to study product, time between onset and last study product administration, and number of study product administrations received.

6.4.3.3 Local laboratory values

Box plots of local laboratory values will be generated for baseline values and for values measured during the course of the study by treatment arm and visit. Each

box plot will show the first quartile, the median, and the third quartile. Outliers (values outside the box plot) will also be plotted. If appropriate, horizontal lines representing boundaries for abnormal values will be plotted.

For each local laboratory measure, summary statistics will be presented by treatment arm and timepoint, as well as changes from baseline for postenrollment values. In addition, the number (percentage) of participants with local laboratory values recorded as meeting Grade 1 AE criteria or above as specified in the Division of AIDS Table for Grading the Severity of Adult and Pediatric Adverse Events (see Section 9.8) will be tabulated by treatment arm for each poststudy product administration timepoint. Reportable clinical laboratory abnormalities without an associated clinical diagnosis will also be included in the tabulation of AEs described above.

6.4.3.4 Reasons for study product administration discontinuation and early study termination

The number and percentage of participants who discontinue study product administration and who terminate the study early will be tabulated by reason and treatment arm.

6.4.4 mAb concentration and PK analysis

6.4.4.1 Primary analyses of mAb concentrations

The primary analysis of serum concentration and PK of PGDM1400LS, VRC07-523LS and PGT121.414.LS (Primary Objective 2) will be restricted to participants who received all scheduled administrations per-protocol. Serum concentrations that fail the quality control of the assay, or from specimens collected outside of the visit window, or from HIV-infected participants postinfection may be excluded. The primary analysis of serum concentration will be descriptive and performed separately for each mAb.

A non-compartmental PK analysis will be performed on the concentration data. PK parameters may include, but are not limited to: area-under-the-curve (AUC), maximum concentration (C_{max}), time to C_{max} (T_{max}), clearance (CL), volume of distribution (Vd), terminal elimination rate constant (λ_z) and the terminal half-life ($T_{1/2}$). For SC Groups, the PK parameters will include AUC, C_{max} , T_{max} , clearance (CL/F, where F is the bioavailability via SC relative to IV), volume of distribution (Vd/F), λ_z and $T_{1/2}$. Data will be summarized by each dose group and overall for CL, Vd and $T_{1/2}$. The potential for non-linear PK among IV or SC recipients will be determined by comparing the dose-adjusted ratios for C_{max} and AUC within IV or SC dosing groups. Graphical displays of the data (eg, boxplots, scatterplots, histograms, spaghetti plots) will be generated to visually explore distributional properties of the data. These summary statistics and graphical displays may be produced for each treatment arm and each time point separately.

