5.1 Primary objectives and endpoints

Primary objective 1:

To evaluate the safety and tolerability of PGDM1400LS when administered via intravenous (IV) or subcutaneous (SC) routes (Part A) and of PGDM1400LS, VRC07-523LS and PGT121.414.LS when administered in sequence IV or SC (Part B)

Primary endpoints 1:

- Local and systemic Solicited AEs, laboratory measures of safety, Unsolicited AEs, and SAEs
- Early discontinuation of administration and reason(s) for discontinuation and early study termination

Primary objective 2:

To evaluate the serum concentrations and pharmacokinetics of PGDM1400LS after a single administration (Part A) and of PGDM1400LS, VRC07-523LS, and PGT121.414.LS after each three-mAb administration (Part B)

Primary endpoint 2:

Serum concentrations of PGDM1400LS, VRC07-523LS and PGT121.414.LS at prespecified timepoints among participants who received all scheduled product administrations

Primary objective 3:

To evaluate the individual mAb-specific serum neutralizing activity after single product administration of PGDM1400LS (Part A) and after each three-mAb administration of PGDM1400LS, VRC07-523LS and PGT121.414.LS (Part B)

Primary endpoint 3:

Magnitude and breadth of neutralizing activity measured with Env pseudotyped viruses specific for either PGDM1400LS, VRC07-523LS or PGT121.414LS in TZM-bl cells at prespecified timepoints among participants who received all scheduled product administrations

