6.4.5 Analysis of neutralization activity and correlation with serum concentrations

6.4.5.1 Primary analyses of neutralization magnitude-breadth curves

To address Primary objective 3, at each specified timepoint, the area-under-the-magnitude-breadth curve (AUC-MB) to a global panel of pseudoviruses (57) will be computed for each participant in the PP cohort with evaluable neutralization ID₅₀ or ID₈₀ data, as described in (58). Magnitude–Breadth (M-B) curves maybe employed to display individual- and group-level response breadth as a function of magnitude. Response breadth is defined as the percentage of viruses in the panel with neutralization titer above certain thresholds. Two choices are to compare the M-B curves among arms, as follows: a non-parametric Wilcoxon rank sum test on the subject-specific area-under-the M-B curve (AUC M-B) or a Kolmogorov-Smirnov type test on the 2 group-average M-B curves. Simulations can be used to obtain 2-sided p-values for the latter test. Second, a weighted-average score-like variable may be constructed to account for the correlations between virus isolates as an integrated magnitude of responses to multiple isolates. Similar group comparison methods described in the first approach may be adopted. Details of either approach will be described in the SAP.

6.4.5.2 Secondary analyses of correlations between serum concentrations and serum neutralization levels

To address Secondary objective 1, pharmacodynamics (PD) models based on either linear or non-linear mixed effects models will be performed to characterize the correlation between serum concentration (observed or popPK model-predicted) and serum neutralization against each virus or the AUC-MB of serum neutralization against the panel. Data from all enrolled participants will be analyzed regardless of how many administrations and how much mAb dose they received (MITT analysis). Similar to the popPK analysis, data from specimens collected outside of the visit window may be included in the PK/PD analyses that account for the actual specimen collection time, and the actual time and dose amount of each product administration. Since the exact date of HIV infection is unknown, any serum level data from blood draws 4 weeks prior to an infected participant's last seronegative sample and thereafter may be excluded. All data from HIV-infected participants who have no seronegative samples postenrollment may be excluded from the analysis.

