7.3.2 Participant departure from study product administration schedule

Every effort should be made to follow the study product-administration schedule per the protocol. If a participant misses a study product administration and the visit window period for the study product administration has passed, that study product cannot be given. The participant should be asked to continue study visits. (see Sections 7.3.1 and 7.3.3).

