7.3.3 Discontinuing study product administration for a participant

Under certain circumstances, an individual participant's study product administrations will be permanently discontinued. Specific events that will result in stopping a participant's study product-administration schedule include:

- Co-enrollment in a study with an investigational research agent (rare exceptions allowing for the continuation of study product administrations may be granted with the unanimous consent of the HVTN 140/HPTN 101 PSRT)
- Clinically significant condition (ie, a condition that affects the immune system or for which continued study product administrations and/or blood draws may pose additional risk), including but not limited to the following:
 - HIV infection
 - Any grade 4 local or systemic Solicited or Unsolicited adverse event (AE) that is subsequently considered to be related to study product administration
 - Grade 3 clinical AE that is subsequently considered to be related to study product administration with the exception of fever, vomiting, and subjective local and systemic symptoms. For grade 3 infusion site erythema and/or induration, upon review, the HVTN 140/HPTN 101 PSRT may allow continuation of study product administration
 - Any grade 3 or 4 lab abnormality confirmed by a repeated value that is subsequently considered to be related to study product;
 - SAE that is subsequently considered to be related to study product administration
 - Clinically significant hypersensitivity or mAb reaction including, but not limited to, type 1 hypersensitivity reaction, urticaria, or serum sickness associated with study product administration. Consultation with the HVTN 140/HPTN 101 PSRT is required prior to subsequent study product administrations following any hypersensitivity reaction associated with study product administration
- Investigator determination in consultation with Protocol Team leadership (eg, for repeated nonadherence to study staff instructions)

Participants discontinuing study product for reasons other than HIV infection should be counseled on the importance of continuing with the study and strongly encouraged to participate in follow-up visits and protocol-related procedures per the protocol for the remainder of the trial, unless medically contraindicated (see HVTN 140/HPTN 101 SSP).

Participants diagnosed with HIV infection during the study should be encouraged to participate in follow-up visits as indicated in Section [9.12](#).

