8.1 Study product regimen

The schedule of study product administration is shown in [Section 1](#) and additional information is given below.

Part A

Group 1: PGDM1400LS 5 mg/kg to be administered via IV infusion at Month 0

Group 2: PGDM1400LS 20 mg/kg to be administered via IV infusion at Month 0

Group 3: PGDM1400LS 20 mg/kg to be administered via SC infusion at Month 0

Group 4: PGDM1400LS 40 mg/kg to be administered via IV infusion at Month 0

Group 5: PGDM1400LS 40 mg/kg to be administered via SC infusion at Month 0

Part B

Group 6: PGDM1400LS 20mg/kg + VRC07-523LS 20mg/kg + PGT121.414.LS 20 mg/kg to be administered via IV infusion sequentially in this order at Month 0 and Month 4

Group 7: PGDM1400LS 20mg/kg + VRC07-523LS 20mg/kg + PGT121.414.LS 20 mg/kg to be administered via SC infusion sequentially in this order at Month 0 and Month 4

Group 8: PGDM1400LS 1.4gram + VRC07-523LS 1.4gram + PGT121.414.LS 1.4gram to be administered via IV infusion sequentially in this order at Month 0 and Month 4

Group 9: PGDM1400LS 1.4gram + VRC07-523LS 1.4gram + PGT121.414.LS 1.4gram to be administered via SC infusion sequentially in this order at Month 0 and Month 4

Group 10: PGDM1400LS 40mg/kg + VRC07-523LS 40mg/kg + PGT121.414.LS 40 mg/kg to be administered via IV infusion sequentially in this order at Month 0 and Month 4

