8 STATISTICAL ANALYSIS

All safety data from enrolled participants will be analyzed according to the initial randomization assignment regardless of how many study product administrations and how much study product they received. Analyses of safety data are modified intent-to-treat (MITT) in that individuals who are randomized but not enrolled do not contribute data and hence are excluded. Because of the brief length of time between randomization and enrollment—typically no more than 4 working days—very few such individuals are expected.

The primary analysis of mAb concentration and anti-viral functional activity data are per-protocol (PP) in that only individuals who receive the expected mAb at the expected dose level within the expected visit window contribute data. Secondary analysis will also involve the MITT cohort, and when necessary account for the actual specimen collection time, and the actual time and dose amount of each product administration.

Analyses for primary endpoints will be performed using SAS and R. Additional software may be used to perform non-compartmental PK and population PK analyses (eg, Monolix). All other descriptive and inferential statistical analyses will be performed using SAS, StatXact, or R statistical software.

No formal multiple comparison adjustments will be employed for multiple primary or secondary endpoints. However, multiplicity adjustments will be made for certain primary or secondary endpoint assays, as discussed below, when the assay endpoint is viewed as a collection of hypotheses (eg, testing multiple pseudo-viruses to determine a positive antiviral functional activity response). Unless otherwise noted, all statistical tests will be 2-sided and will be considered statistically significant if $p < 0.05$.

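### In Part B, dose-1 samples count in the primary PK and neutralization analyses only if the participant later receives infusion #2 in window

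*Protocol*

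**What the plan says.** Primary endpoints 2 (serum concentrations) and 3 (neutralization) in Protocol 5.1 are measured "at prespecified timepoints among participants who received all scheduled product administrations". SAP 3.1 repeats this wording. Protocol 6.4.4.1 states that the primary PK analysis "will be restricted to participants who received all scheduled administrations per-protocol". In 6.4.5.1 the area under the magnitude-breadth curve "will be computed for each participant in the PP cohort with evaluable neutralization" data.

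The general per-protocol definition in Protocol 6.4, repeated in SAP 8, is that "only individuals who receive the expected mAb at the expected dose level within the expected visit window contribute data". It classifies people, with no separate rule for each dose or timepoint.

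Each Part B group receives the three mAbs "sequentially in this order at Month 0 and Month 4" (Protocol 8.1). Appendix L allows infusion #2 from 14 days before to 14 days after Day 112. Once that window has passed, "that study product cannot be given" (7.3.2), although the participant is asked to keep attending visits.

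The secondary analyses also use the MITT cohort (6.4, SAP 8), and secondary endpoint 1 takes participants however many doses they received.

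**The concern.** Primary objective 2 asks for serum concentrations and PK in Part B "after each three-mAb administration (Part B"), and objective 3 asks the same of neutralization. Dose 1 is thus a target in its own right. Its samples are complete before infusion #2 is given, so nothing that happens at Month 4 can alter them. The plan nevertheless uses what happens at Month 4 to decide whether they count.

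Two things are at stake. First, the condition can be informative. The reasons in 7.3.3 for stopping product include related adverse events, confirmed related laboratory abnormalities and "Clinically significant hypersensitivity or mAb reaction including, but not limited to, type 1 hypersensitivity reaction, urticaria, or serum sickness". Dose-1 exposure would then be summarized only in people who went on to be re-dosed. Second, dose 2 cannot replace what is lost. Day 3 and Day 6 samples are drawn only after infusion #1, and the Day 116 contact after infusion #2 is by phone without specimens (Appendix G). Early concentrations, which matter most for peak level and time to peak after SC dosing, come mainly from dose 1.

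**Working it through.** **Who is removed.** The table follows a Part B participant correctly given infusion #1 who does not receive infusion #2 in its window.

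| Timepoint (Appendices G, I, L) | Affected by infusion #2? | In primary set now? | In a dose-specific set? |
|---|---|---|---|
| Day 0, 3, 6, 28, 56, pre-infusion Day 112 | No | No | Yes |
| Post-infusion Day 112, Day 168, 224, 280 | Yes | No | No |

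Part A is untouched because it has one administration. The rule concerns Groups 6-10: 5 × 16 = 80 participants.

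**The plan's own precision figure.** Protocol 6.1.2 uses a two-sided 95% t interval on the log scale: exp[log(10) ± t(0.975, n−1) × SD/√n]. With SD 0.5 and n = 12, the half-width is 2.201 × 0.5/√12 = 0.3177. This gives (7.3, 13.7) mcg/mL, as in Table 6-3. The stated 20% loss from 16 is 16 × 0.8 = 12.8; the plan uses 12.

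**Effect of the rule on precision.** The documents give no rate of dose-2 non-receipt, so 1 or 2 of 16 per group is an assumption. Half-widths at SD 0.5:

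| n | Log half-width | 95% CI at 10 mcg/mL |
|---|---|---|
| 11 | 0.3359 | (7.1, 14.0) |
| 12 | 0.3177 | (7.3, 13.7) |
| 13 | 0.3021 | (7.4, 13.5) |
| 14 | 0.2887 | (7.5, 13.3) |

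- If the excluded participants are already among those lost in going from 16 to 12, keeping them gives n = 13 or 14. The half-width narrows by 1 − 0.3021/0.3177 = 4.9% or 1 − 0.2887/0.3177 = 9.1%.
- If their loss comes on top of the 20% allowance, a dose-specific set has about 13 (12.8 rounded) and the current rule leaves 12 or 11. Keeping them narrows the half-width by 4.9% or by 1 − 0.3021/0.3359 = 10.1%.

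Both readings give about 5-10%. The percentages are the same at SD 1.0, because SD cancels in the ratio.

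**Effect of the rule on the estimate.** Let a fraction q be excluded and let retained minus excluded mean log concentration be Δ. The primary geometric mean then differs from that of all correctly dosed participants by the factor exp(qΔ). The documents supply neither q nor Δ. Purely to show the scaling, a gap of one planning SD (Δ = ±0.5) gives exp(±0.5/16) = 1.03 or 0.97 with 1 of 16 excluded, and exp(±1.0/16) = 1.06 or 0.94 with 2 of 16.

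**The case against.** A per-protocol primary analysis with a secondary MITT analysis is a common, disclosed choice. The primary PK analysis is descriptive, so no hypothesis test rests on it. A participant who is modestly late for infusion #2 is still inside the ±14-day window and is not removed. SAP 1 expects later revisions covering these assays. All of this stands. It limits the consequence but does not remove the conflict with the objective. The secondary analyses do not correct the primary estimate, and neither document sets out a dose-1 non-compartmental or descriptive summary in the MITT cohort.

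Some stronger readings are tempting but unsupported:

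- *The dose-1 data are thrown away.* They leave the primary analysis only.
- *The loss is about 12%, or 2 of 16.* Protocol 4.8.5 reports 440 IV or SC administrations in HVTN 127/HPTN 087 against 100 × 5 = 500 scheduled, or 88%. That covers five doses in a study listed as ongoing and is not a dose-2 rate. If every first dose was given and a constant share dropped out before each later dose (assumed), a retention of 0.936 reproduces it: 1 + 0.936 + 0.876 + 0.820 + 0.768 = 4.400 doses per person. That is 6.4% without dose 2, about 1 of 16.
- *The rule inflates exposure.* Section 7.3.3 has no stopping criterion based on PK or anti-drug antibodies, and 10.1 keeps research assay results away from treatment decisions. Reactions could accompany high exposure as readily as fast clearance.
- *The 20% allowance ignores this loss.* Section 6.1 names early termination among its reasons, so part of the loss is already counted.
- *Only dose 1 is well sampled.* Dose 2 lacks Day 3 and Day 6 samples but is followed for 24 weeks, against 16 for dose 1.

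One could also argue that the wording in 6.4 and SAP 8 was meant to apply dose by dose. The endpoint definitions in 5.1 and the restriction in 6.4.4.1 say otherwise, so the passages would still need reconciling.

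**Conclusion.** The point holds for Part B. As written, primary PK and neutralization results at dose-1 timepoints are conditional on later receiving infusion #2 in window. This does not match the objective of evaluating each administration, and the condition can be tied to product reactions.

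The main issue is this dependence on a later event; the precision cost is modest. With 1 or 2 of 16 per group affected (an assumption), retaining them would narrow the half-width by about 5-10%. Selection bias is possible, but the documents support neither a direction nor a size. The plan's stated sample sizes and confidence intervals are not in error on this point.

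**What to change.** Define the per-protocol set by administration:

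- Dose-1 timepoints, Day 0 through the pre-infusion Day 112 sample: everyone who received infusion #1 as assigned, whatever happened afterwards.
- Timepoints after infusion #2: those who received both infusions as assigned.

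Make the change in primary endpoints 2 and 3 (Protocol 5.1 and their copy in SAP 3.1), Protocol 6.4, 6.4.4.1 and 6.4.5.1, and SAP 8. The PK and neutralization revision that SAP 1 anticipates is a convenient place for the detail. The handling of out-of-window specimens in 6.4.4.1 is permissive and a separate matter, so it need not change for this purpose.

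The cost is revised wording and one additional population flag. Denominators will differ between dose-1 and dose-2 tables, so each table should state its own n, and comparisons of dose 1 with dose 2 should say whether they use only participants who received both.

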This trial is designed to evaluate both SC and IV routes, as SC administration may be more feasible than IV in some settings, and the comparison of these routes will elucidate the bioavailability of PGDM1400LS SC vs. IV and, thus, inform future decisions regarding dose, frequency and route of PGDM1400LS administration. Toward informing future dosing decisions, the trial is also designed to evaluate both weight-based and fixed dosing. The fixed dose of 4.2 g of total mAb (1.4 g of each mAb) would be equivalent to a weight-based dose of 60 mg/kg of total mAb (20 mg/kg each) for a 70 kg participant; 70 kg is the approximate median of participants' baseline weights in the AMP studies (38). A PK model of administration of a 4.2 g fixed dose underscores the comparability of this dose to a 60 mg/kg dose in terms of coverage at an ID80 >200 (see Figure 4-5).

The effect of body weight on drug biodistribution has been observed for some monoclonal antibodies (39-43), but body-weight-based dosing is not clearly necessary in human adults, who have a body size range of generally only 2- to 3-fold (44, 45). When body weight has a significantly less than proportional effect on PK parameters, body-weight-based dosing may over-adjust for the body size effect. Fixed dosing simplifies administration, potentially enhancing safety by reducing dosing errors, and it can be more cost-effective and convenient to manufacture and administer. Of note, the anti-SARS-CoV-2 mAbs in late-stage clinical trials or post-EUA are administered in fixed doses (evaluated at up to 8 g total per administration), as are many mAbs used for oncologic and anti-inflammatory indications. Whether fixed dosing is equivalent to body-weight-based dosing for a given mAb is unknown until studied in the target population (eg, adult humans) and there is a growing call to assess it early in clinical development programs. (44-46).

[figure not shown]

Figure 4-3 Relationship between neutralization titers and level of prevention efficacy. (A) In humans in the AMP studies, predicted ID₈₀ serum neutralizing titer is calculated as the median VRC01 concentration at mid-infusion visits (35.0 µg/ml) divided by IC₈₀ (concentration from BAMA) of the acquired virus (n=162 infected cases) from the AMP trials. The median concentration was computed based on the n=82 non-case VRC01 recipients from both dose arms sampled for PK modeling ([name], unpublished data). (B) In a meta-analysis of NHP receiving a single bnAb (37).

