¹²SST blood will be collected at specific time points after the onset of any Ab reaction. Refer to the SSP for more information.

¹³The 56-day total blood volume does not include up to 51mL SST blood collected for any Ab reaction; however, the 56-day limit is not exceeded at any visit by the possible collection of SST blood for an Ab reaction.

¹⁴Of this volume, 8.5mL of SST blood will be **collected post study product administration** (see SSP for details).

¹⁵Pregnancy test at enrollment does not need to be performed if negative results are received from screening pregnancy test conducted within 48 hours prior to study product administration .

¹⁶Phone contact only. No specimen collection at this visit.

y = SST blood collected for serum storage will also cover specimen needs for drug concentrations, HIV-1 neutralizing Ab assays, non-neutralizing antiviral assays, and ADA detection and functional assays (including for any Ab reactions); no separate blood draw is needed.

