Appendix L Visit windows

Part A

Visit Number	Visit Type	Lower Allowable Window	Lower Target Day	Target Day	Upper Target Day	Upper Allowable Window
01.0	Screening	-56	-		-	-
02.0	Enrollment¹ Infusion	-	-	0	-	-
03.0	3 days post infusion	-1	-	3	-	+1
04.0	6 days post infusion	-1	-	6	-	+2
05.0	4 weeks post infusion	-7	-3	28	+3	+7
06.0	8 weeks post infusion	-7	-3	56	+3	+7
07.0	16 weeks post infusion	-7	-3	112	+3	+7
08.0						
09.0	24 weeks post infusion	-7	-3	168	+3	+7

Greyed-out visit does not apply to Part A.

Part B

Visit Number	Visit Type	Lower Allowable Window	Lower Target Day	Target Day	Upper Target Day	Upper Allowable Window
01.0	Screening	-56	-		-	-
02.0	Enrollment Infusion #1	-	-	0	-	-
03.0	3 days post infusion #1	-1	-	3	-	+1
04.0	6 days post infusion #1	-1	-	6	-	+2
05.0	4 weeks post infusion #1	-7	-3	28	+3	+7
06.0	8 weeks post infusion #1	-7	-3	56	+3	+7
07.0	Infusion #2	-14	-7	112	+7	+14
08.0	4 days post infusion #2	-	-	116	+7	-
09.0	8 weeks post infusion #2	-7	-3	168	+3	+7
10.0	16 weeks post infusion #2	-7	-3	224	+3	+7
11.0	24 weeks post infusion #2	-7	-3	280	+3	+7

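### Non-compartmental PK is not limited to a dose, but after infusion 2 there is no blood between the post-administration tube and week 8, so dose-2 SC Cmax, Tmax and AUC cannot be estimated that way

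*Protocol*

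**What the plan says.** Protocol 5.1 (repeated in SAP 3.1) sets primary objective 2 as serum concentrations and PK, in Part B "after each three-mAb administration (Part B"). Primary endpoint 2 is narrower: concentrations at prespecified timepoints in participants who received every scheduled administration.

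The only PK method set out is in Protocol 6.4.4.1: "A non-compartmental PK analysis will be performed on the concentration data". The general list is permissive ("PK parameters may include, but are not limited to: area-under-the-curve (AUC), maximum concentration"). The list for subcutaneous arms is a commitment ("For SC Groups, the PK parameters will include AUC") and goes on to Cmax, Tmax, CL/F, Vd/F, the terminal rate constant and half-life. Neither list says which infusion or interval it applies to.

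Appendix G and Appendix L fix the sampling. On each infusion day one 8.5 mL tube is "collected post study product administration", with the clock time left to the SSP. After infusion 1, further samples come on Days 3, 6, 28, 56 and 112. After infusion 2, the Day 116 visit is a phone contact without specimens. The next blood is at "8 weeks post infusion #2" (Day 168), then Days 224 and 280.

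Population PK appears in Protocol 6.4 and SAP 8 as something for which software may be used, and in passing in Protocol 6.4.5.2. No model is specified. The current SAP has no PK section.

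**The concern.** A non-compartmental analysis sees only what is sampled. After infusion 2 the first eight weeks hold one tube, taken on the infusion day. For an SC arm that tube precedes most absorption, so the rise, the peak and most of the early decline go unseen. For an IV arm the tube catches the peak, but one straight or log-linear segment then has to bridge distribution and 56 days of elimination. Drug left from dose 1 is also still present.

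The parameters at risk are dose-2 SC Cmax, Tmax, AUC and CL/F, dose-2 IV AUC and CL, and any accumulation ratio built from them. If dose-2 AUCs were also used to compare routes, the errors would compound, because SC is read low and IV is read at or above its true value.

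**Working it through.** **1. Is there a hidden draw?** The Appendix G volumes say no.
- Day 112: serum 51 mL, of which 8.5 mL is post-administration, leaving 42.5 mL, taken here as the pre-dose draw. Visit total 51 + 5 + 5 + 10 = 71 mL.
- Day 116: 0. Day 168: 42.5 + 5 + 5 = 52.5. Day 224: 42.5. Day 280: 42.5 + 5 + 5 + 10 = 62.5.
- 56-day totals: 71 + 0 = 71; 71 + 52.5 = 123.5 (printed as 124); 52.5 + 42.5 = 95; 42.5 + 62.5 = 105. All match.

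The protocol gives no accuracy figure for AUC, Cmax or Tmax to reproduce.

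**2. Inputs.**
- From the protocol: VRC07-523LS half-life 38 days IV (4.8.4); PGDM1400 19.4 days (4.8.2), with LS variants predicted 2-3 times longer (4.5.2), so 38.8-58.2 days; doses 112 days apart.
- Assumed, not in the documents: terminal half-life range rounded to 38-60 days; V1 3 L, V2 2.7-3 L, Q 0.5-0.8 L/day; first-order SC absorption, ka 0.15-0.5 per day; no assay noise.

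**3. Hand example.** One compartment, half-life 38 days, λ = ln2/38 = 0.01824; absorption half-life 2 days, ka = 0.3466; concentrations in units of (bioavailable dose)/V.

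SC: f(t) = ka/(ka − λ) × [exp(−λt) − exp(−ka·t)], with ka/(ka − λ) = 1.0556. Concentration t days after dose 2 is f(t) + f(t + 112).
- Pre-dose: 0.137. Tube at 0.1 day: 0.171. Week 8: 0.429. Week 16: 0.155.
- Linear trapezoid, 0-112 days: 0.1 × (0.137 + 0.171)/2 + 55.9 × (0.171 + 0.429)/2 + 56 × (0.429 + 0.155)/2 = 0.02 + 16.77 + 16.35 = 33.1.
- True area, the integral of f from 0 to 224: 1.0556 × [(1 − 0.0168)/0.01824 − 1/0.3466] = 53.85.
- AUC read at 33.1/53.85 = 62% of truth.
- True peak 0.966 at day 8.6; highest sample 0.429 at day 56. Cmax read at 44%, Tmax at 56 days.

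IV, same disposition: samples 1.130, 0.407, 0.146. Linear trapezoid 28 × (1.130 + 0.407) + 28 × (0.407 + 0.146) = 58.5 against a true 53.9, so +9%. A log-down rule is exact for this curve, so 0%.

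**4. Two-compartment range.** Clearance is solved to give the target terminal half-life; both doses are superposed; sample grids are 0, 3, 6, 28, 56, 112 days (dose 1) and 0, 56, 112 days (dose 2). Values are % of truth, AUC over 0-112 days:

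| | Linear | Linear-up/log-down |
|---|---|---|
| Dose 1 IV AUC | 103-106 | 101-102 |
| Dose 1 SC AUC | 99-105 | 97-101 |
| Dose 2 IV AUC | 134-163 | 122-134 |
| Dose 2 SC AUC | 55-73 | 53-72 |

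Dose-2 SC Cmax is read at 30-67% of truth. SC Tmax is always read as 56 days, against a true 3-14 days. In these SC curves 63-74% of the interval's exposure falls in the unsampled first eight weeks.

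**5. Sensitivity.** A separate parameterisation used AUC over 0-168 days, a fast phase of 0 to 50% of the initial concentration, and absorption half-lives of 1-3.5 days. At a 38-day half-life it gives dose-2 SC AUC −32 to −40%, SC Cmax −50 to −73%, IV AUC +9 to +48% (linear) or 0 to +26% (log-down), and IV Cmax 0 to −2%. At 58.2 days SC AUC is −22 to −28% and IV AUC +4 to +30% (linear) or 0 to +19% (log-down).

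**The case against.** The case against is that this attacks an analysis the plan never states. Section 6.4.4.1 does not say that AUC, Cmax and Tmax will be computed separately for dose 2. Section 6.1.2 calls objective 2 descriptive, to be met by estimating mean concentrations at timepoints, which the dose-2 samples support. Population PK is foreseen, and SAP section 1 expects later revisions. No sample-size calculation, safety rule or decision rule rests on dose-2 AUC.

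Much of that stands, and it rules out several stronger readings that a reader might reach:
- **That AUC, Cmax and Tmax are all biased, in opposite directions by route.** Opposite directions applies to AUC only. The post-administration tube catches IV Cmax to within about 2%, and IV Tmax with it.
- **That IV AUC is badly wrong in any case.** The error depends on an unstated trapezoid rule and on the distribution phase. With a log-down rule and mono-exponential decline it is zero.
- **That the SC-versus-IV bioavailability estimate is lost.** Protocol 4.5.1 says "the comparison of these routes will elucidate the bioavailability of PGDM1400LS SC vs. IV". Part A (Group 2 against 3, 4 against 5) and Part B dose 1 (Group 6 against 7, 8 against 9) supply that comparison with adequate sampling for AUC.
- **That primary endpoint 2 fails, or objective 2 must be restated.** Timepoint concentrations are unaffected.
- **That the tube is taken at end of infusion.** The protocol says only that it follows administration.

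What does not stand is the inference that silence is harmless. The objective covers each administration, nothing confines the method to dose 1, and the SC parameter list is mandatory. No trapezoid rule recovers an SC peak that was never sampled.

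**Conclusion.** The mismatch is real and should be fixed before PK analysis starts, but it is confined to dose-2 non-compartmental parameters. Under half-lives of 38-60 days and ka of 0.15-0.5 per day, dose-2 SC Tmax is read as 56 days, SC Cmax at about 30-70% of truth, and SC AUC roughly 25-45% low. IV AUC is too high by about 0 to 60%, depending on the trapezoid rule and distribution phase. The SC conclusions are robust to model choice in direction and rough size; the IV size is not. Dose-1 AUC is within about 5-6% of truth, so the route comparison has a sound source. Dose-1 SC peaks are less exact if absorption is slow, since nothing is drawn between Days 6 and 28: Cmax was up to 16% low in the cases tried.

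**What to change.** In Protocol 6.4.4.1, and in the SAP revision that adds PK:
1. Limit non-compartmental AUC, Cmax, Tmax, CL (CL/F) and Vd (Vd/F), and any SC:IV bioavailability or dose-proportionality comparison, to Part A and Part B dose 1. State the interval and trapezoid rule.
2. For dose 2, report observed concentrations (pre-dose, post-administration, +8, +16 and +24 weeks) and the terminal half-life from the last three.
3. Take dose-2 exposure and clearance from a prespecified population PK model fitted jointly to both doses, using actual dose amounts, dose times and sample times.

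The cost is wording and model specification; population PK software is already named, and no visit or blood draw is added. The downside is that dose-2 exposure becomes model-based. If an observed dose-2 profile is wanted instead, draws 3, 6 and 28 days after infusion 2 would be needed. At a 38-day half-life these bring SC AUC error to between −3 and +6%. They cost three extra draws; at 42.5 mL each the Day 112-168 total becomes 71 + 127.5 + 52.5 = 251 mL, under the 500 mL limit.
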